8.4 ADVERSE EVENTS AND SERIOUS ADVERSE EVENTS

8.4.1 DEFINITION OF ADVERSE EVENTS (AE)

For this protocol, an **adverse event (AE)** is any untoward medical occurrence (e.g., sign, symptom, disease, syndrome, intercurrent illness, clinically significant abnormal laboratory finding, injury or

accident) that emerges or worsens following administration of investigational product and until the end of trial participation that may not necessarily have a causal relationship to the administration of the investigational product. An AE can therefore be any unfavorable and/or unintended sign (including a clinically significant abnormal laboratory result), symptom, or disease temporally associated with the use of an investigational product, whether or not considered related to the investigational product. A treatment-emergent AE is one that occurs after any period of exposure to treatment.

Pre-existing conditions, which increase in frequency or severity or a change in nature as a consequence of an investigational product use will also be considered an adverse event.

An unexpected AE is an adverse reaction, the nature or severity of which is not consistent with the applicable product information (e.g., Investigator's Brochure for an unapproved investigational product or package insert/summary of product characteristics for an approved product).

Any clinically significant change in the study safety evaluations, (e.g., vital signs, laboratory results, ECG, injection site evaluation, physical/neurological examinations, etc.) post-treatment must be reported as an AE.

8.4.2 DEFINITION OF SERIOUS ADVERSE EVENTS (SAE)

A **serious adverse event (SAE)** is any untoward medical occurrence that results in any of the following outcomes:

- Death
- Life-threatening, (i.e., the subject was, in the opinion of the Investigator, at immediate risk of death from the event as it occurred. It does not apply to an AE that hypothetically might have caused death if it were more severe)
- Persistent or significant disability/incapacity or substantial disruption of the subject's ability to carry out normal life functions
- Requires in-patient hospitalization or prolongs hospitalization (i.e., a prolonged hospitalization beyond the expected length of stay; hospitalizations for elective medical/surgical procedures, scheduled treatments, or routine check-ups are not SAEs by this criterion)
- Congenital anomaly/birth defect (i.e., an adverse outcome in a child or fetus of a subject exposed to the molecule or investigational product before conception or during pregnancy)
- Does not meet any of the above serious criteria but based upon appropriate medical judgement may jeopardize the subject or may require medical or surgical intervention to prevent one (1) of the outcomes listed above (i.e., is a significant or important medical event)

8.4.3 CLASSIFICATION OF AN ADVERSE EVENT

8.4.3.1 SEVERITY OF EVENT

The Investigator is responsible for evaluating all AEs and determining the severity of the event. Severity will be categorized as mild, moderate or severe according to the following definitions:

- **Mild:** Event may be noticeable to subject; does not influence daily activities; usually does not require intervention
- **Moderate:** Event may be of sufficient severity to make subject uncomfortable; performance of daily activities may be influenced; intervention may be needed

- **Severe:** Event may cause severe discomfort; usually interferes with daily activities; subject may not be able to continue in the trial; treatment or other intervention usually needed

8.4.3.2 RELATIONSHIP TO STUDY INTERVENTION

Relationship of an AE to investigational product will be assessed as follows:

- **Definite:** There is a clinically plausible time sequence between the onset of the AE and the administration of investigational product; when the event responds to withdrawal of investigational product and/or recurs with re-administration of investigational product
- **Probable:** There is a clinically plausible time sequence between the onset of the AE and the administration of investigational product; the AE is unlikely to be caused by the concurrent/underlying illness, other drugs or procedures
- **Possible:** There may or may not be a clinically plausible time sequence between the onset of the AE and the administration of investigational product and a cause cannot be ruled out
- **Unrelated:** There is not a temporal or causal relationship to investigational product administration

8.4.3.3 EXPECTEDNESS

The Medical Monitor and Sponsor will be responsible for determining whether an adverse event (AE) is expected or unexpected. An AE will be considered unexpected if the nature, severity, or frequency of the event is not consistent with the risk information previously described for the study intervention.

Expectedness is further defined in the Investigator's Brochure (IB) under Anticipated Risks and Side Effects. The list of AEs found in the IB can be considered to be expected AEs.

8.4.4 TIME PERIOD AND FREQUENCY FOR EVENT ASSESSMENT AND FOLLOW-UP

The occurrence of an adverse event (AE) or serious adverse event (SAE) may come to the attention of study personnel during study visits and interviews of a study participant presenting for medical care, or upon review by a study monitor.

All AEs including local and systemic reactions not meeting the criteria for SAEs will be captured on the appropriate case report form (CRF). Information to be collected includes event description, time of onset, clinician's assessment of severity, relationship to study product (assessed only by those with the training and authority to make a diagnosis), and time of resolution/stabilization of the event. All AEs occurring while on study must be documented appropriately regardless of relationship. All AEs will be followed to adequate resolution.

Any medical condition that is present at the time that the participant is screened will be considered as baseline and not reported as an AE. However, if the study participant's condition deteriorates at any time during the study, it will be recorded as an AE.

Changes in the severity of an AE will be documented to allow an assessment of the duration of the event at each level of severity to be performed. AEs characterized as intermittent require documentation of onset and duration of each episode.

The Investigator or study staff will record all reportable events with start dates occurring any time after informed consent is obtained until 7 (for non-serious AEs) or 30 days (for SAEs) after the last day of study participation. At each study visit, the Investigator or study staff will inquire about the occurrence of

AE/SAEs since the last visit. Events will be followed for outcome information until resolution or stabilization.

8.4.5 ADVERSE EVENT REPORTING

The Investigator will assess subjects post-treatment and at each subsequent trial visit for the occurrence of AEs. In order to avoid bias in eliciting AEs, subjects should be asked the following non leading question: “How have you felt since your last visit?” All AEs (serious and non-serious) reported by the subject must be recorded on the source documents and CRFs.

In addition, an Investigator must report an SAE to Revance within **24 hours** of their awareness of the event according to the procedure outlined below. All fatal or life-threatening SAEs should be telephoned to Revance or the authorized representative as soon as the Investigator learns of the event.

8.4.6 SERIOUS ADVERSE EVENT REPORTING

An Investigator must report an SAE to Revance or the designated CRO’s authorized representative within **24 hours** of their awareness of the event:

1. Complete and return an SAE Form with all information known to date; including the Investigator’s assessment of causality.
2. If the event is fatal or life-threatening, telephone Revance or the authorized representative as soon as the Investigator learns of the event.
3. Obtain and maintain all pertinent medical records (discharge summary, autopsy report, etc.) and medical judgments of medical personnel who assisted in subject’s treatment and follow-up.
4. Provide follow-up information to Revance or the authorized representative.

All SAEs will be followed until satisfactory resolution or until the Investigator deems the event to be chronic or the participant is stable. Other supporting documentation of the event may be requested by the Data Coordinating Center (DCC)/study sponsor and should be provided as soon as possible.

The study sponsor will be responsible for notifying the Food and Drug Administration (FDA) of any unexpected fatal or life-threatening suspected adverse reaction as soon as possible, but in no case later than 7 calendar days after the sponsor’s initial receipt of the information. In addition, the sponsor must notify FDA and all participating investigators in an Investigational New Drug (IND) safety report of potential serious risks, from clinical trials or any other source, as soon as possible, but in no case later than 15 calendar days after the sponsor determines that the information qualifies for reporting.

Regulatory authorities, IRBs/IEC, and Investigators will be notified of SAEs in accordance with applicable regulations and requirements (e.g., GCPs, ICH Guidelines, national regulations and local requirements).

8.4.7 REPORTING EVENTS TO PARTICIPANTS

Revance will disclose clinical trial data to individuals, to investigators at clinical sites, and publicly as aggregate summaries, in accordance to Regulatory and local legal requirements.

8.4.8 FOLLOW-UP OF NON-SERIOUS ADVERSE EVENTS

Non-serious AEs that are identified during the last scheduled trial visit (or early discontinuation, if applicable) must be recorded on the AE CRF as ongoing.

Any clinically significant abnormal test results, e.g., laboratory findings, at the Week 16/Early Termination visit should be followed to resolution or until determined by the Investigator to be stabilized. Repeat tests may be indicated to establish this.

If a subject has any clinically significant, trial-related abnormalities at the end of the trial, the Medical Monitor should be notified and every effort made by the Investigator to arrange follow up evaluations at appropriate intervals to document the course of the abnormalities.

8.4.9 FOLLOW-UP OF POST TRIAL SERIOUS ADVERSE EVENTS

SAEs that are identified on the last scheduled contact (or early discontinuation, if applicable) must be recorded on the AE CRF page and reported to the CRO and Revance according to the reporting procedures outlined in Section 8.4.6. This may include unresolved previously reported SAEs, or new SAEs. The Investigator should follow these SAEs until the events are resolved, or the subject is lost to follow-up. The Investigator should continue to report any significant follow-up information to the Medical Monitor, Revance, and the IRB/IEC up to the point the event has been resolved. Resolution means the subject has returned to the baseline state of health, or the Investigator does not expect any further improvement or worsening of the subject's condition.

Any new SAEs reported by the subject to the Investigator that occur after the last scheduled contact and are determined by the Investigator to be reasonably associated with the administration of investigational product should be reported to Revance and the IRB/IEC.

[Redacted text]

[Redacted text]

[Redacted text]

- [Redacted text]
- [Redacted text]

[Redacted text]

- [Redacted text]
- [Redacted text]

- [Redacted text]
- [Redacted text]

[figure not shown]
- [Redacted text]
- [Redacted text]

- [Redacted text]
- [Redacted text]

- [Redacted text]
- [Redacted text]

- [Redacted text]
- [Redacted text]

- [Redacted text]
- [Redacted text]

8.4.11 REPORTING OF PREGNANCY

During the trial, all WOCBP should be instructed to contact the Investigator immediately (within 24 hours) if they suspect they might be pregnant (e.g., missed or late menstrual cycle). The Investigator must immediately notify Revance or designated Contract Research Organization (CRO) of any female subject who becomes pregnant any time during study participation, record the information on the Pregnancy Notification Form and send the form to the CRO. The site will be asked to follow-up with the subject periodically during the pregnancy for ongoing health and safety information through term, as applicable. Subjects will remain on the trial.

8.5 UNANTICIPATED ADVERSE EVENTS

8.5.1 DEFINITION OF UNANTICIPATED ADVERSE EVENTS

The Office for Human Research Protections (OHRP) considers unanticipated problems involving risks to participants or others to include, in general, any incident, experience, or outcome that meets **all** of the following criteria:

- Unexpected in terms of nature, severity, or frequency given (a) the research procedures that are described in the protocol-related documents, such as the Institutional Review Board (IRB)-approved research protocol and informed consent document; and (b) the characteristics of the participant population being studied;
- Related or possibly related to participation in the research (“possibly related” means there is a reasonable possibility that the incident, experience, or outcome may have been caused by the procedures involved in the research); and
- Suggests that the research places participants or others at a greater risk of harm (including physical, psychological, economic, or social harm) than was previously known or recognized

Revance will comply with these criteria for reporting Unanticipated Adverse Events.

8.5.2 UNANTICIPATED ADVERSE EVENT REPORTING

The Investigator will report unanticipated Adverse Events to the reviewing Institutional Review Board (IRB) and the Sponsor. The unanticipated adverse event report will include the following information:

- Protocol identifying information: protocol title and number, PI’s name, and the IRB project number;
- A detailed description of the event, incident, experience, or outcome;
- An explanation of the basis for determining that the event, incident, experience, or outcome represents an unanticipated adverse event;
- A description of any changes to the protocol by the Sponsor or other corrective actions that have been taken or are proposed in response to the unanticipated adverse event.
- The Sponsor will update the IB or provide Dear Doctor letter should these actions be deemed required.

To satisfy the requirement for prompt reporting, unanticipated adverse events will be reported using the following timeline:

- Unanticipated adverse events that are fatal and life-threatening serious adverse events (SAEs) will be reported to the IRB and to the Sponsor within seven (7) days of the Investigator becoming aware of the event.
- Any other unanticipated adverse events that are SAEs will be reported to the IRB and to the Sponsor within 15 days of the Investigator becoming aware of the problem.
- All unanticipated adverse events that non-serious AEs are not required to be reported to the IRB or to the Sponsor.
- All unanticipated serious adverse events should be reported to appropriate institutional officials (as required by an institution's written reporting procedures), the supporting agency head (or designee), and the Office for Human Research Protections (OHRP) if applicable.

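### Protocol 8.5.2 waives reporting of non-serious unanticipated adverse events to the IRB and sponsor, against its own opening sentence and the definition adopted in 8.5.1

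*Protocol*

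**What the plan says.** Section 8.5.1 of the protocol takes over the OHRP definition of an unanticipated problem. An event must meet all three criteria:

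- it is unexpected ("Unexpected in terms of nature, severity, or frequency given (a) the research procedures that are described in the protocol-related documents" and for the population studied);
- it is related or possibly related to the research;
- it carries a risk implication ("Suggests that the research places participants or others at a greater risk of harm" than was known before).

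The section ends with a commitment: "Revance will comply with these criteria for reporting Unanticipated Adverse Events".

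Section 8.5.2 opens with a rule that has no seriousness limit: "The Investigator will report unanticipated Adverse Events to the reviewing Institutional Review Board (IRB) and the Sponsor". It then lists timelines for prompt reporting: 7 days for fatal and life-threatening unanticipated SAEs, and 15 days for other unanticipated SAEs. The third bullet reads: "All unanticipated adverse events that non-serious AEs are not required to be reported to the IRB or to the Sponsor".

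Other sections bear on where a non-serious event goes. Section 8.4.4 says "All AEs including local and systemic reactions not meeting the criteria for SAEs will be captured on the appropriate case report form (CRF"). Section 8.4.5 says "All AEs (serious and non-serious) reported by the subject must be recorded on the source documents and CRFs". Section 8.4.3.3 gives the judgement of expectedness to others than the site: "The Medical Monitor and Sponsor will be responsible for determining whether an adverse event (AE) is expected or unexpected".

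**The concern.** The bullet takes out of the reporting rule a class of events that the definition puts in. The class matters. To qualify under 8.5.1 at all, an event must already suggest that participants face more risk than was recognised. An ordinary non-serious AE, expected or without implication for risk, is not an unanticipated event and was never due for this kind of report.

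Section 7.1 states that each subject is treated once only and that discontinuation of treatment does not apply. News of an unexpected event therefore chiefly protects subjects who have not yet been injected, and it does so only if it arrives in time. Section 8.5.2 ties the report to corrective action: it must describe protocol changes and other measures taken or proposed, and the sponsor may update the Investigator's Brochure or write to investigators. An exempt event does not enter that process through 8.5.2.

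**Working it through.** This is a comparison of texts. No stated figure has to be reproduced and no arithmetic applies.

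**Step 1: does the definition depend on seriousness?** No. The criteria in 8.5.1 are unexpectedness, relatedness and implied greater risk. The first mentions severity, but only as one respect in which an event may be unexpected. Seriousness is defined separately in 8.4.2 and is not referred to.

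**Step 2: do the rules in 8.5.1 and 8.5.2 agree?** Take an event that meets all three criteria.

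| Event | 8.5.1 commitment | 8.5.2 opening sentence | 8.5.2 timeline |
|---|---|---|---|
| Fatal or life-threatening SAE | covered | report to IRB and sponsor | 7 days |
| Other SAE | covered | report to IRB and sponsor | 15 days |
| Non-serious | covered | report to IRB and sponsor | no report required |

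The first two rows are consistent across the columns. The third is not. The bullet conflicts both with the commitment in 8.5.1 and with the first sentence of its own section.

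**Step 3: does another visible route carry a non-serious unanticipated event promptly?**

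- *To the IRB.* The other visible routes for individual events are limited to SAEs: Section 8.3 under assessment of adverse events, 8.4.6, and 8.4.9 for SAEs at or after the last contact. None covers a non-serious event.
- *To the sponsor by CRF.* The event is recorded (8.4.4, 8.4.5). The only visible deadline for forwarding data is in 10.1.9.1.1, which requires all of it by study termination at the latest.
- *To the Medical Monitor.* Section 8.4.8 asks for notification of clinically significant, trial-related abnormalities at the end of the trial. It does not cover events during follow-up.
- *To the DMC.* Section 10.1.6 gives the committee a safety review during the study, but places its evaluation of the data after all subjects have been recruited, at times set in the Charter. Review at that stage cannot inform the enrolment of further subjects.
- *To FDA and all investigators.* Section 8.4.6 requires the sponsor to notify them of potential serious risks within 15 calendar days of deciding that the information qualifies. This is not confined to serious events, but it starts only once the sponsor knows of the event.

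**Step 4: what is lost and what is kept?** Recording is kept. So is the final analysis: SAP 4.7.2 lists all AEs and summarises all treatment-emergent ones whatever their seriousness, so AE frequencies in the report are not affected. What is lost is the prompt report to the sponsor and, in the visible text, any individual-event route to the IRB. There is also a knock-on effect. Section 8.4.3.3 has the Medical Monitor and sponsor judge expectedness, and the bullet removes the prompt report that would put the event before them.

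**The case against.** The best defence is that the bullet sits in a list introduced as serving prompt reporting, so it may be meant to waive only the expedited report. The sentence is also visibly garbled, and an event that need not be reported may still be reported. This stands as a possible reading of intent. It does not settle the text: the waiver is unqualified, and 8.5.2 offers no later timeline for these events. If a limited waiver was meant, the section has to say so.

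A second defence is that the sponsor sees the events anyway, through CRFs, monitoring and visits at Weeks 1, 2, 4, 8 and 16. That is correct, and it limits the consequence to delay. It gives the IRB nothing, and no prompt deadline is visible.

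Third, text is blacked out after the assessment of adverse events in 8.3 and between 8.4.9 and 8.4.11. A further reporting route may lie there, so its absence cannot be asserted. Such a route would not remove the contradiction between 8.5.1 and 8.5.2.

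A reader might infer more: that the bullet removes the early signal of toxin effect at the dose under test. The documents do not support this. They show no dose, and the events are still elicited, recorded and open to sponsor and DMC review. A reader might also reach for an example such as weakness away from the injected leg. Whether that would be unexpected depends on the Investigator's Brochure, which 8.4.3.3 makes the reference and which is not among the documents.

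**Conclusion.** The point holds as an internal contradiction in a safety-reporting rule. Sections 8.5.1 and 8.5.2 give opposite instructions for a non-serious event that meets all three criteria. Followed literally, the bullet leaves such an event without a prompt report to the sponsor and, in the visible text, without an individual-event route to the IRB. The signal may be delayed; it is not lost.

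The size can be stated only in kind: one of the three classes of unanticipated event in 8.5.2 has no reporting requirement. The documents give no rate for such events, so any count or probability would rest wholly on an assumption and would still not measure delay or harm. The conclusion assumes that the bullet is read as written and that the redacted text holds no separate prompt route for these events. The contradiction itself depends on neither the redacted text nor any rate. It should be corrected by amendment, because a site following the stated rule would be entitled not to report events that by definition suggest more risk than was known.

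**What to change.** Delete the third timeline bullet in 8.5.2. In its place state that any event meeting all three criteria in 8.5.1, serious or not, is reported to the IRB and the sponsor, and have the sponsor set a time limit for the non-serious ones beside the existing 7-day and 15-day limits. Add that non-serious AEs which do not meet the three criteria stay on the CRF only.

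The same amendment should reconcile a related conflict. Section 8.5.2 allows 7 or 15 days for unanticipated SAEs to reach the sponsor, while 8.4.5 and 8.4.6 require every SAE to reach the sponsor in 24 hours.

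The cost is a short protocol amendment with IRB approval, a note to sites, and a few extra reports in a trial of about 60 subjects. No analysis, sample size or visit changes.
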